## 11.5.3 Analysis of Primary and Exploratory Immunogenicity End Points

Immunogenicity will be summarized according to the treatment group to which the subject was randomized.

Immunogenicity samples will be drawn for all subjects. Immunogenicity analyses will be based upon results from appropriately sized subsets of samples, according to the purpose. The statistical analysis of immunogenicity results will be primarily based on the evaluable immunogenicity sets. An additional analysis will be performed based on the all-available sets if there is a large enough difference in sample size between the all-available immunogenicity set and the evaluable immunogenicity set.

Immunogenicity will be summarized by the total set (active vs. placebo).

Endpoint	Statistical Analysis Methods
Primary (Key Immunogenicity Endpoints)	All measures will be analyzed comparing the two active vaccine groups. The immunogenicity set will be used for this analysis. All results will be presented descriptively and summarized by treatment groups.
	.For specific primary immunogenicity endpoints please refer to Section 8.2- Immunogenicity Assessments- Primary Immunogenicity Assessments:
Exploratory	All measures will be analyzed comparing the two active vaccine groups. The immunogenicity set will be used for this analysis. All results will be presented descriptively and summarized by treatment groups. The analysis of these bio samples is optional. For specific exploratory immunogenicity endpoints please refer to Section
	8.2-Immunogenicity Assessments- Exploratory Immunogenicity Assessments

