#### Immunogenicity:

- Serum Anti-VP1 GI.1 IgA and Anti-VP1 GII.4 IgA by Meso Scale Discovery (MSD) assay by dose level
  - o geometric mean concentration (GMC) at Day 1 and Day 29
  - o geometric mean fold rise (GMFR) from Day 1 to Day 29
- Serum Anti-VP1 GI.1 IgG and Anti-VP1 GII.4 IgG by Meso Scale Discovery (MSD) assay by dose level
  - o geometric mean concentration (GMC) at Day 1 and Day 29
  - o geometric mean fold rise (GMFR) from Day 1 to Day 29
- Serum Antibody BT50 titers for both GI.1 and GII.4 by Histo-blood group antigen (HBGA) Assay
  - o geometric mean titer (GMT) Day 1 and Day 29
  - o geometric mean fold rise (GMFR) from Day 1 to Day 29

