#### **Primary Immunogenicity Assessments:**

- Serum –Anti IgA for both GI.1 and GII.4 by Meso Scale Discovery (MSD) assay by dose level
  - o geometric mean concentration (GMC) at Day 1 and Day 29
  - o geometric mean fold rise (GMFR) from Day 1 to Day 29

Vaxart Inc		
VXA-NVV-202	Version	2.0

- Serum-Antibody titers for both GI.1 and GII.4 by Histo-blood group antigen (HBGA)-Blocking Assay (BT50) –
  - o geometric mean titer (GMT) Day 1 and Day 29
  - o geometric mean fold rise (GMFR) from Day 1 to Day 29
- Serum Anti- IgG for both GI.1 and GII.4 by MSD assay
  - $\circ$  geometric mean concentration (GMC) at Day 1 and Day 29
  - o geometric mean fold rise (GMFR) from Day 1 to Day 29

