#### Table 9:Populations for Analyses

Analysis Population	Description
Screened	All subjects who enter screening (assigned a screening number)
Intent to Treat (ITT)	All subjects who are randomized. The analyses using ITT will be based upon the randomization group allocated.
Per Protocol	All subjects in the ITT set who receive one dose and who have not violated any inclusion/exclusion criteria and / or deviated in a way that could influence their Immunogenicity assessments.

Analysis Population	Description
Safety	All randomized subjects who receive at least 1 dose of the study drug. Subjects will be analyzed according to the treatment (vaccine) they actually received. All safety analyses will be conducted based on the Safety set.
Immunogenicity	All randomized subjects who receive at least 1 dose of the study drug and have at least one valid immunogenicity result after Day 1. Subjects will be analyzed according to the treatment (vaccine) they actually received. All immunogenicity analyses will be conducted based on the Immunogenicity set.

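### Section 11.5.3 promises a comparison of the two doses but names no high:medium ratio, no immunogenicity interval and no Day 1 adjustment, and the protocol contradicts itself on the analysis set and grouping

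*Combined protocol and SAP*

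**What the plan says.** The primary objective (Synopsis; Section 3.1.1) is to determine safety and immunogenicity so as to choose the dose level for Phase 3. For primary and exploratory immunogenicity alike, the table in Section 11.5.3 says "All measures will be analyzed comparing the two active vaccine groups", and then "All results will be presented descriptively and summarized by treatment groups".

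The primary measures (Sections 3.2.1 and 8.2) cover six analytes: serum IgA, serum IgG and BT50, each for GI.1 and GII.4. For the four IgA and IgG analytes they are "geometric mean concentration (GMC) at Day 1 and Day 29" and "geometric mean fold rise (GMFR) from Day 1 to Day 29". BT50 has the same structure with titers (GMT).

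Section 11.1 plans no hypothesis testing. Section 11.5.2 names Clopper-Pearson 95% CIs for safety proportions. Sections 11 and 11.5.1 call this material a summary. They leave full detail, including analysis sets and missing data, to an SAP to be finalized before database lock and unblinding.

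On grouping, Section 11.5.3 says "Immunogenicity will be summarized according to the treatment group to which the subject was randomized". Table 9 says of the Immunogenicity set "Subjects will be analyzed according to the treatment (vaccine) they actually received", and requires only that subjects "have at least one valid immunogenicity result after Day 1". Section 11.5.3 also bases the analysis primarily on evaluable sets, with a possible further analysis on all-available sets, and allows results to come from subsets of samples.

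**The concern.** The high-versus-medium contrast is the immunogenicity evidence for the dose choice. As written, a reader would have per-arm summaries but no estimate of the between-dose difference and no statement of its uncertainty. Each analyte also offers two between-dose readouts, the Day 29 level and the fold rise. Over six analytes that makes twelve, with no stated priority. Day 1 enters the dose comparison only as the divisor of the fold rise.

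The second problem lies in the protocol text itself. The same immunogenicity analysis is grouped as randomized in one place and as received in another. It is assigned to evaluable sets, to all-available sets and to the immunogenicity set, and Table 9 defines only the last. Whoever writes the SAP must choose between conflicting instructions.

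**Working it through.** **Text check.** The current text of Sections 3, 8.2 and 11 contains no between-dose ratio or difference, no interval for an immunogenicity measure, and no model or covariate. There is no current power or precision figure to reproduce. The 2:2:1 split of 125 gives 50, 50 and 25, as stated.

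**Inputs.** n = 50 per active arm comes from Section 11.2. Everything else is assumed, because the documents give no SD or correlation: Day 29 log10 SD s from 0.3 to 0.6, Day 1 to Day 29 correlation r from 0.3 to 0.7, and Day 29:Day 1 SD ratio k of 1, 1.25 or 1.5.

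**Width of the unstated interval.** The 95% CI is the ratio multiplied or divided by 10^(t × SD × √(2/n)), where √(2/50) = 0.2.

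| Contrast | SD used | Narrowest | Widest |
|---|---|---|---|
| Day 29 GMC/GMT ratio (98 df) | s | 1.32 (s = 0.3) | 1.73 (s = 0.6) |
| GMFR ratio, k = 1 (98 df) | s√(2 − 2r) | 1.24 (s = 0.3, r = 0.7) | 1.91 (s = 0.6, r = 0.3) |
| ANCOVA on Day 1 (97 df) | s√(1 − r²) | 1.22 (s = 0.3, r = 0.7) | 1.69 (s = 0.6, r = 0.3) |

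Section 11.5.3 allows assays on subsets, so 50 is an upper limit. With an illustrative 25 assayed per arm, √(2/25) = 0.283 on 48 df and the GMC factor becomes 1.48 to 2.19.

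**Gain from using Day 1.** The contrast variances are proportional to k² (GMC), k² + 1 − 2rk (GMFR) and k²(1 − r²) (ANCOVA).

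- Against GMC the cut is r²: 9%, 25% and 49% at r = 0.3, 0.5 and 0.7.
- Against GMFR at k = 1 the cut is (1 − r)/2: 35%, 25% and 15%.
- Against GMFR at k = 1.25 it is 22%, 11% and 2%.
- Against GMFR at k = 1.5 it is 13%, 4% and 0.2%.

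The gain over GMFR can therefore be close to nothing. In large samples with equal arms, ANCOVA is never less precise than either unadjusted contrast.

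**How often the two readouts point to different doses.** With no true difference, the correlation between the log GMC ratio and the log GMFR ratio is ρ = (k − r)/√(k² + 1 − 2rk), and the chance of opposite signs is arccos(ρ)/π. At k = 1, r = 0.3 this is arccos(0.592)/π = 30%; at k = 1, r = 0.7 it is arccos(0.387)/π = 37%. The range is 25% to 29% at k = 1.25 and 21% to 23% at k = 1.5.

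With a true difference, the bivariate normal probability (n = 50, all three values of k) is 5% to 24% at a true ratio of 1.25, 0.2% to 11.5% at 1.5, and at most 2% at 2.

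**The case against.** The strongest reply is that Section 11 is expressly a summary. Model, interval and covariate are normal SAP content, and missing-data handling is assigned to the SAP by name. That stands: their absence here does not show that the final plan lacks them, and the same holds for a missing Day 1 value.

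A second reply is that the trial is descriptive, so side-by-side tables are a fair reading of the comparison, and fold rise already uses baseline. This also stands in part. A reader might infer that the planned comparison is biased or ignores baseline. The documents do not support that: both unadjusted contrasts are unbiased under randomization, and Day 1 values are tabulated, so an imbalance would be visible. However, a descriptive design does not preclude intervals. Section 11.5.2 gives them for safety, and a ratio with a CI is estimation, not a test.

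A reader might also take the 21% to 37% disagreement as the chance of choosing the wrong dose. It is not. It applies only when neither dose is truly better on that analyte, and it shrinks quickly as a real difference appears.

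Finally, the randomized-versus-received conflict changes results only if someone receives another arm's product, and Section 6.8 has dosing supervised and checked by a second person. That limits its weight, but the texts still need to agree.

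**Conclusion.** The point holds as a gap in specification together with an internal inconsistency. The protocol promises the dose comparison that its objective needs but does not say what will be estimated or with what uncertainty. Under the assumed SDs and correlations, that uncertainty is material: a factor of roughly 1.2 to 1.9 either way with 50 assayed per arm, and more if subsets are assayed.

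Day 1 adjustment is an inexpensive improvement, not the correction of an error. It supplies one main readout per analyte. It does not remove the other readouts, settle disagreement between analytes or weigh safety.

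The conflicts over grouping and analysis sets stand on the text alone and need no assumption. This should be fixed before unblinding; it does not threaten the validity of the trial. Confidence is medium, because the SAP is not in the file.

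**What to change.** Before unblinding, in Section 11.5.3 or the SAP:

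- For each of the six primary analytes, prespecify the high:medium geometric mean ratio at Day 29 with 95% CI, from an ANCOVA of log10 Day 29 on dose and log10 Day 1 in the two randomized active arms. Name it the main descriptive dose contrast, with no hypothesis test.
- Keep per-arm GMC/GMT and GMFR, with 95% CIs, as supporting tables.
- Name one analysis set and one grouping, as randomized, for this contrast. Align Table 9 with Section 11.5.3, and define or delete the evaluable and all-available sets.
- State the number assayed per arm.
- Have the SAP's missing-data rule cover a missing Day 1 value. Filling it with the pooled mean log10 Day 1 of the two active arms is one option, not a requirement.

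The cost is one SAP paragraph, six small models, one table of ratios and a wording alignment in the protocol. No added subjects, samples or data are needed.

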#### 11.5.4 Baseline descriptive Statistics

Demographic data, baseline characteristics, physical examination, concomitant medications, medical history data and study medication exposure will be summarized by treatment group.

## 11.5.5 Sub-group Analysis

The primary endpoint will be summarized and analyzed by the following subgroups using the ITT set:

The primary endpoint will be summarized and analyzed by the following subgroups using the ITT set:

- Age
  - Up to and including age 65 years
  - Age 66 years and older
- Sex
- Race

#### 11.5.6 Tabulation of Individual Subject Data

By subjects listing will be produced for each variable by treatment group and study visit.

# **12. ETHICAL CONSIDERATION**

#### 12.1 Ethical Conduct of the Study

The study will be conducted in accordance with the protocol, legal and regulatory requirements, and the general principles set forth in the International Ethical Guidelines for Biomedical Research Involving Human Subjects (Council for International Organizations of Medical Sciences [CIOMS] 2002), ICH Guideline for Good Clinical Practice, and the Declaration of Helsinki.

#### **12.2 Institutional Review Board**

It is the responsibility of the Investigator to have prospective approval of the study protocol, protocol amendments, informed consent documents, and other relevant documents, e.g., recruitment advertisements, if applicable, from the IRB/IEC. All correspondence with the IRB/EC should be retained in the Investigator file.

The only circumstance in which an amendment may be initiated prior to IRB/IEC approval is where the change is necessary to eliminate apparent immediate hazards to the subjects. In that event, the Investigator must notify the IRB/IEC and Sponsor in writing immediately after the implementation.

They should also be informed of any event likely to affect the safety of the subjects or the continued conduct of the clinical study, in particular any change in safety. All updates to the IB will be sent to the IRB/IEC and to Health Authorities (Competent Regulatory Authority), as required by local regulation. A progress report is sent to the IRB/IEC at least annually and a summary of the study's outcome at the end of the clinical study.

#### **12.3 Inform Consent Process**

Informed consent is a process that is initiated prior to the individual's agreeing to participate in the study and continues throughout the individual's study participation. Consent forms will be Institutional Review Board (IRB)-approved and the subject will be asked to read and review the document. The Investigator will explain the research study to the subject and answer any questions that may arise. A verbal explanation will be provided in terms suited to the subject's comprehension of the purposes, procedures, and potential risks of the study and of their rights as research subjects. Subjects will have the opportunity to carefully review the written consent form and ask questions prior to signing.

Vaxart Inc		
VXA-NVV-202	Version	2.0

The subjects should have the opportunity to discuss the study with their family or surrogates or think about it prior to agreeing to participate. The subject will sign the informed consent document prior to any procedures being done specifically for the study. Subjects must be informed that participation is voluntary and that they may withdraw from the study at any time, without prejudice. A copy of the informed consent document will be given to the subjects for their records. The informed consent process will be conducted and documented in the source document (including the date), and the form signed, before the subject undergoes any study-specific procedures. The rights and welfare of the subjects will be protected by emphasizing to them that the quality of their medical care will not be adversely affected if they decline to participate in this study.

If the trial is involving vulnerable population, video recording of entire informed consent process should be ensured depending on the norms of respective country's regulatory authorities.

## **12.4 Insurance Compensation**

The Sponsor certifies that it has taken out a liability insurance policy covering all clinical trials under its sponsorship. This insurance policy is in accordance with local laws and requirements. The insurance of the Sponsor does not relieve the Investigator and the collaborators from any obligation to maintain their own liability insurance policy. An insurance certificate will be provided to the IRB/IEC or regulatory authorities in countries requiring this document.

## 12.5 Stipends/Rewards/Compensation for Participation

Subjects may be provided with a stipend according to local practice to compensate for the time and travel required for study visits and procedures.

# 12.6 Subject Confidentiality

Subject confidentiality and privacy will be strictly held in trust by the participating Investigators, their staff, and the Sponsor and their interventions. This confidentiality is extended to cover testing of biological samples in addition to the clinical information relating to subjects. Therefore, the study protocol, documentation, data, and all other information generated will be held in strict confidence. No information concerning the study or the data will be released to any unauthorized third party without prior written approval of the Sponsor. All research activities will be conducted in as private a setting as possible.

The study monitor, other authorized representatives of the Sponsor, representatives of the Institutional Review Board (IRB), regulatory agencies or pharmaceutical company supplying study product may inspect all documents and records required to be maintained by the investigator, including but not limited to, medical records (office, clinic, or hospital) and pharmacy records for the Subjects in this study. The clinical study site will permit access to such records.

The study subject's contact information will be securely stored at each clinical site for internal use during the study. At the end of the study, all records will continue to be kept in a secure location for as long a period as dictated by the reviewing IRB, Institutional policies, or Sponsor requirements.

Study subject research data, which is for purposes of statistical analysis and scientific reporting, will be transmitted to and stored at sponsors designated vendor. This will not include the subject's contact or identifying information. Rather, individual Subjects and their research data will be identified by a unique study identification number. The study data entry and study management systems used by clinical sites and by designated vendor research staff will be secured and password protected. At the end of the study, all study databases will be de-identified and archived

# 12.7 Reporting of Safety Issues and Serious Breaches of the Protocol or ICH GCP

In the event of any prohibition or restriction imposed (i.e., clinical hold) by an applicable regulatory authority in any area of the world, or if the Investigator is aware of any new information that might influence the evaluation of the benefits and risks of the investigational product, Sponsor should be informed immediately.

In addition, the Investigator will inform Sponsor immediately of any urgent safety measures taken by the Investigator to protect the study subjects against any immediate hazard, and of any serious breaches of this protocol or of ICH GCP that the Investigator becomes aware of.

# 13. Data Handling and Record Keeping

# **13.1 Source Documents**

Source data are all information, original records of clinical findings, observations, or other activities in a clinical trial necessary for validation of the clinical data. Examples of these original documents and data records include, but are not limited to, hospital records, clinical and office charts, laboratory notes, memoranda, subjects' memory aid or evaluation checklists, pharmacy dispensing records, recorded data from automated instruments, copies or transcriptions certified after verification as being accurate and complete, microfiches, photographic negatives, microfilm
or magnetic media, x-rays, and subject files and records kept at the pharmacy, at the laboratories, and medico-technical departments involved in the clinical trial. All information on the CRF will be traceable to these source documents, which are generally maintained in the subject's study file.

The source documents will include a copy of the signed Informed Consent/ Health Insurance Portability and Accountability Act (HIPAA) authorization. The source document data collection forms for screening. Outpatient visits and AEs will also serve as CRF data collection instruments.

The Investigator is responsible for ensuring the accuracy, completeness, legibility, and timeliness of the data reported. Source documents are maintained for recording data for each subject enrolled in this clinical trial. Study subjects' data collected on the CRF during the trial will only be identified by subject number. If, as an exception, it is necessary for safety or regulatory reasons to identify the subject, both the Sponsor and the Investigator are bound to keep this information confidential.

# 13.2 Case Report Forms (CRF)

As used in this protocol, the term CRF should be understood to refer to either a paper form or an electronic data record or both, depending on the data collection method used in this trial.

A CRF is required and should be completed for each included subject. The completed original CRFs are the sole property of Vaxart and should not be made available in any form to third parties, except for authorized representatives of Vaxart or appropriate regulatory authorities, without written permission from Vaxart.

The Investigator has ultimate responsibility for the collection and reporting of all clinical, safety, and laboratory data entered on the CRFs and any other data collection forms (source documents) and ensuring that they are accurate, authentic/original, attributable, complete, consistent, legible, timely (contemporaneous), enduring, and available when required.

The CRFs must be signed by the Investigator or by an authorized staff member to attest that the data contained on the CRFs are true. Any corrections to entries made in the CRFs or source documents must be dated, initialed, and explained (if necessary) and should not obscure the original entry.

# 13.3 Data Collection and Management Responsibility

Data collection is the responsibility of the clinical trial staff at the site under the supervision of the site Investigator. The Investigator is responsible for ensuring the accuracy, completeness, legibility, and timeliness of the data reported.

All source documents should be completed in a neat, legible manner to ensure accurate interpretation of data. Hardcopies of the study visit worksheets will be provided for use as source document worksheets for recording data for each subject enrolled in the study.

Data recorded in the eCRF)/ (CRF)derived from source documents should be consistent with the data recorded on the source documents.

Clinical data (including adverse events (AEs, concomitant medications, and expected adverse reactions data) and clinical laboratory data will be entered into an data capture system that is 21 CFR Part 11-compliant. The data system includes password protection and internal quality checks, such as automatic range checks, to identify data that appear inconsistent, incomplete, or inaccurate. Clinical data will be entered directly from the source documents.

# **13.4 Record Retention**

Study documents should be retained for a minimum of 10 years after the last approval of a marketing application in an International Conference on Harminosation (ICH region and until there are no pending or contemplated marketing applications in an ICH region or until at least 10 years have elapsed since the formal discontinuation of clinical development of the study drug.

These documents should be retained for a longer period, however, if required by local regulations. No records will be destroyed without the written consent of the Sponsor, if applicable. It is the responsibility of the Sponsor to inform the Investigator when these documents no longer need to be retained.

